Site personnel will transmit ECG data to an ECG central laboratory for central processing and reading by a qualified cardiologist (central reader) who, also blinded by study drug assignment, will independently review each ECG. QT interval corrected for heart rate (QTc) will be determined using Fridericia's correction method (QTcF). The central ECG laboratory's data will be entered into the database. The central reader will also provide the interpretation of the ECG (i.e., "Normal" or "Abnormal"). The central ECG laboratory will send the ECG report to the site within 3 business days. The Investigator (or physician designee) will review the central reader's report/assessment and document his/her review by signing and dating the central ECG laboratory report. The investigator should review and reconcile if necessary his/her interpretation of the ECG

(normal/abnormal) with the central ECG laboratory in case of relevant divergent assessments and reconcile as he/she determines is appropriate.

ECGs will be collected as single ECGs as follows:

Cohort 1 Subjects:

- **Screening**
- **Day 1 (Dose 1)**
 - Pre-dose (just prior to the start of infusion) and within 15 minutes after the end of infusion prior to the PK sample collection)
- **Days 5 and 15**
 - Collection should be scheduled as close as possible to the corresponding time of the post infusion collection on Day 1.
- **Days 29 and 57 (Doses 2 and 3)**
 - Pre-dose (just prior to the start of infusion)
- **Day 85 (Dose 4)**
 - Pre-dose (just prior to the start of infusion) and within 15 minutes after the end of infusion (prior to the PK sample collection)
- **Weeks 24, 36, 48, and 72 (Doses 7, 10, 13 and 19 respectively)**
 - Pre-dose (just prior to the start of infusion)
- **Week 96 (Study Completion Visit)**
- **Follow-up (Week 104)**

Cohort 2 Subjects:

- **Screening**
- **Day 1 (Dose 1)**
 - Pre-dose (just prior to the start of infusion) and approximately within 15 minutes after the end of infusion).
- **Days 29, 57, 85 and Weeks 24, 36, 48, and 72 (Doses 2, 3, 4, 7, 10, 13 and 19 respectively)**

- Pre-dose (just prior to the start of infusion).
- **Week 96 (Study Completion Visit)**
- **Follow-up (Week 104)**

Urine Screens for Drugs of Abuse

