Randomization Visit). At the computation level, the value of "baseline" for an efficacy or safety assessment is determined using the Rx Day associated with the visit. Namely, baseline value is determined by taking the last non-missing observation obtained before the time of first dosing on Rx Day 1. If an SAE occurs on the first dosing day, the event will be reported as a post-baseline event and the related safety assessments will be considered post-baseline data as well.

Definition of Analysis Windows

To perform longitudinal data analysis, observations that are obtained after the first day of study drug administration will be assigned to an analysis "week" associated with the Rx Days that are corresponding to the observations. Unless otherwise specified, efficacy observations and safety observations no more than 45 days after the last dose of study drug will be included in analyses for the double-blind period. Safety observations later than 45 days, but no more than 20 weeks, after the last dose of study drug will be included for the post-treatment follow-up period safety analysis. The intervals presented below for each scheduled visit (Rx Days X through Y) include both Rx Days X and Y. The nominal day for each scheduled visit is defined in "Days of Study Activities" row in [Table 2](#).

For measurements that are planned to be collected during the double-blind treatment period at Weeks 24, 48, 72 and 96, i.e., CDR, RBANS, ADAS-Cog-14, MMSE, FAQ and NPI, observations will be mapped to an analysis "week" according to the following windows defined by Rx day.

- Week 24 Rx Days 2 through 252
- Week 48 Rx Days 253 through 420
- Week 72 Rx Days 421 through 588
- Week 96 Rx Days > 588

For measurements that are planned to be collected during the double-blind treatment period at Weeks 48 and 96, i.e., UPSA-Brief, ADCS-CGIC-MCI and ADCS-MCI-ADL-

24, observations will be mapped to an analysis "week" according to the following windows defined by Rx day.

- Week 48 Rx Days 2 through 504
- Week 96 Rx Days > 504

For measurements that are planned to be collected during the double-blind treatment period at Weeks 4, 8, 12, 16, 20, 24, 28, 32, 36, 40, 44, 48, 52, 56, 60, 64, 68, 72, 76, 80, 84, 88, 92 and 96, i.e., body weight, observation will be mapped to an analysis "week" according to the following windows defined by Rx day.

- Week 4 Rx Days 2 through 42
- Week 8 Rx Days 43 through 70
- Week 12 Rx Days 71 through 98
- Week 16 Rx Days 99 through 126

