- Week 16 Rx Day 99 through 126
- Week 20 Rx Days 127 through 154
- Week 24 Rx Days 155 through 210
- Week 36 Rx Days 211 through 294
- Week 48 Rx Days 295 through 378
- Week 60 Rx Days 379 through 462
- Week 72 Rx Days 463 through 546
- Week 84 Rx Days 547 through 630
- Week 96 Rx Days > 630

For measurements that are planned to be collected during the double-blind treatment period at Weeks 2, 4, 8, 12, 24, 36, 48, 72 and 96, i.e., ECG, observation will be mapped to an analysis "week" according to the following windows defined by Rx day.

- Week 2 Rx Days 2 through 21 (Cohort 1 subjects)
- Week 4 Rx Days 22 through 42 (Cohort 1 subjects)
Rx Days 2 through 42 (Cohort 2 subjects)
- Week 8 Rx Days 43 through 70
- Week 12 Rx Days 71 through 126
- Week 24 Rx Days 127 through 210
- Week 36 Rx Days 211 through 294
- Week 48 Rx Days 295 through 420
- Week 72 Rx Days 421 through 588
- Week 96 Rx Days > 588

For vital sign measurements, C-SSRS, ECG, clinical laboratory tests, and MRI that are planned to be collected during the post-treatment follow-up period at Weeks 104, observations will be mapped to an analysis "week" according to the following windows defined by Rx End day.

- Post-Treatment Week 8 Rx End Days > 45

For measurements that are planned to be collected during double-blind treatment period on Weeks 6, 14, 30, 46, 70 and 96, i.e., MRI observation will be mapped to an analysis "week" according to the following windows defined by Rx day.

- Week 6 Rx Days 2 through 70
- Week 14 Rx Days 71 through 154
- Week 30 Rx Days 155 through 266
- Week 46 Rx Days 267 through 406
- Week 70 Rx Days 407 through 581

- Week 96 Rx Days > 581

If more than 1 observation is included in a visit time window, the observation that is closest to the nominal day of the visit will be used in the analysis. If two observations have the same distance to the nominal day of the visit, the last non-missing observation will be used in analyses. If more than 1 observation occurs on the same day, the average will be calculated and used in analyses.

7.0 Demographics, Baseline Characteristics, Subject History, and Previous/Concomitant Medications

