11.5.2 Potentially Clinically Significant ECG Values

Criteria for potentially clinically significant values have been predefined for selected ECG variables as outlined in [Appendix C](#). For each variable, a summary of the number and percentage of subjects in each treatment group who have at least one double-blind observation that meets the PCS criteria and is more extreme than their baseline value will be provided. Listings will also be prepared to include all observations for each variable for each subject that meet the PCS criteria for that variable at any time during the study. No comparisons of treatment groups will be performed.

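### No by-visit ECG result shows the end-of-infusion change in full: the Day 1 tracing falls in no analysis window, and the Day 85 tracing is averaged with the pre-dose one

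*SAP*

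**What the plan says.** **Collection (Protocol 5.3.1.1, 12-Lead ECG).** In Cohort 1 there are two ECGs on Day 1, one pre-dose and one "within 15 minutes after the end of infusion prior to the PK sample collection". The same pair is repeated on Day 85. In Cohort 2 the pair is taken on Day 1 only, the second tracing "approximately within 15 minutes after the end of infusion". Every other dosing-day ECG in both cohorts is pre-dose. The remaining tracings are Days 5 and 15 (Cohort 1), Week 96 and Week 104.

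**Windows (SAP 6.2).** For longitudinal analysis, "observations that are obtained after the first day of study drug administration will be assigned to an analysis" week. The first ECG window is "Week 2 Rx Days 2 through 21 (Cohort 1 subjects") in one cohort and Week 4, "Rx Days 2 through 42 (Cohort 2 subjects"), in the other. Day 85 lies in Week 12 (Rx Days 71 to 126). Baseline is the last value before first dosing.

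**Several values in one window (SAP 6.2).** The value nearest the nominal day is used. Then comes a tie rule: "If two observations have the same distance to the nominal day of the visit, the last non-missing observation will be used in analyses". Then the same-day rule: "If more than 1 observation occurs on the same day, the average will be calculated and used in analyses".

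**Analyses.** SAP 11.5.1 gives mean change from baseline to each visit and to the minimum, maximum and final double-blind value, each dose against placebo. SAP 11.5.2 counts subjects with "at least one double-blind observation that meets the PCS criteria and is more extreme than their baseline value". The criteria in SAP Appendix C are QTcF above 499 ms and an increase above 60 ms.

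**The concern.** The end-of-infusion ECGs are the only ones timed close to peak serum concentration. That is an inference from intravenous dosing and from SAP 12.1, which treats Cmax as missing unless a sample was drawn within 3 hours after the end of infusion. If the antibody had an acute effect on QTcF, PR or heart rate, these are the tracings most likely to show it.

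The SAP chose to compare ECG change with placebo visit by visit. Its own rules then leave the Day 1 end-of-infusion tracing without a visit and blend the Day 85 one with a trough tracing. A reader of the by-visit table could take it as evidence on the whole dosing interval, when it contains no undiluted end-of-infusion result.

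**Working it through.** The plan gives no sample size, power or precision figure for ECGs, so there is nothing to reproduce. The check maps each scheduled ECG to the SAP 6.2 windows and then applies the multiple-value rules.

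**Step 1: mapping.**

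| Scheduled ECG | Cohort 1 | Cohort 2 |
|---|---|---|
| Day 1 pre-dose | baseline | baseline |
| Day 1 end of infusion | no window | no window |
| Days 5, 15 | Week 2 | not taken |
| Day 29, Day 57 pre-dose | Week 4, Week 8 | Week 4, Week 8 |
| Day 85 pre-dose | Week 12 | Week 12 |
| Day 85 end of infusion | Week 12, same day | not taken |
| Weeks 24, 36, 48, 72 pre-dose | own week | own week |
| Week 96 | Week 96 | Week 96 |

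**Step 2: counts.** Inputs are about 400 subjects (SAP 4.3) and 48 in Cohort 1 (SAP 4.2), so Cohort 2 is 400 − 48 = 352.

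- End-of-infusion ECGs planned: 48 × 2 + 352 × 1 = 448.
- Day 1, no window: 400 / 448 = 89%.
- Day 85, averaged with pre-dose: 48 / 448 = 11%.
- At full weight in a by-visit comparison: 0.

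**Step 3: size of the dilution on Day 85.** Let p be the pre-dose change from baseline and a the further change from pre-dose to end of infusion. The end-of-infusion change is p + a. The averaged value is (p + p + a)/2 = p + a/2, so the acute part is halved: a = 10 ms shows as 5 ms. It is the acute part that is halved, not the whole change from baseline, because the Day 85 pre-dose tracing is at trough and not drug-free.

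SAP 11.5.1 names no split by cohort. If Week 12 is tabulated over both cohorts, about 12 of 100 subjects per arm contribute an averaged value and the rest a pre-dose one. The acute effect then enters the arm mean with weight 0.5 × 12/100 = 0.06, so 10 ms becomes 0.6 ms.

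**Step 4: PCS, conditional on averaging.** Take baseline and pre-dose QTcF of 430 ms and an end-of-infusion value of 500 ms. The individual tracing meets both criteria (500 > 499; +70 > 60). The average is (430 + 500)/2 = 465 ms, a change of +35 ms, and meets neither. This matters only if PCS uses averaged values, which the SAP does not say.

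**Step 5: what separate time points would give.** The 95% half-width for a dose-placebo difference is 1.96 × SD × √(2/n). The documents give no SD of QTcF change; 10 to 20 ms is assumed.

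- Day 1, n about 100 per arm: 2.8 ms (SD 10) to 5.5 ms (SD 20).
- Day 85, n about 12 per arm (48/4): 8 ms to 16 ms.

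**The case against.** **The minimum, maximum and PCS results already capture these tracings.** This largely stands as a limit on the point. The averaging rule closes a subsection on longitudinal windows. SAP 11.5.2 counts any qualifying double-blind observation and lists every observation meeting the criteria. Protocol 8.1.6.4 counts PCS values at any time after the first dose. SAP 6.2 separately brings safety observations up to 45 days after the last dose into the double-blind analyses. A reader might infer that the SAP hides PCS values by averaging, or that its ECG tables describe trough exposure only. The text supports neither: individual tracings are the more natural reading for PCS, and the Day 5 and Day 15 ECGs in Cohort 1 are not trough values. What remains is that the averaging sentence is written for analyses in general, with no exemption in 11.5, so the data source for minimum, maximum and PCS is unstated. Even on the favourable reading, a maximum taken over all times cannot isolate an end-of-infusion effect.

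**The tie rule would select the Day 85 end-of-infusion ECG.** Two same-day tracings are equally distant from the nominal day, so this reading is possible. The same-day rule is the more specific and should govern, but no order of precedence is given. The tie rule does nothing for Day 1.

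**The protocol promises no by-visit ECG comparison.** True: Protocol 8.1.6.4 specifies change to final and PCS, and the synopsis adds minimum and maximum. By-visit means are an SAP addition, so this is not a departure from the protocol. Nor do the documents say that these ECGs were meant to detect an acute infusion effect; Protocol 5.6.2 gives early detection of safety signals as the reason for the denser Cohort 1 schedule. Local and central ECG reading and unblinded DMC review serve that aim during the trial. They do not make the final by-visit table informative at end of infusion.

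**Conclusion.** The point holds for the by-visit analysis in SAP 11.5.1. About 400 Day 1 end-of-infusion ECGs are neither baseline nor part of any visit. Up to 48 Day 85 end-of-infusion ECGs enter Week 12 at half weight. No by-visit result shows the end-of-infusion change in full, and in Cohort 2 no end-of-infusion ECG reaches any visit.

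The Day 1 part follows directly from the windows. The Day 85 part rests on the same-day rule prevailing over the tie rule. The counts assume full enrolment and complete collection, and about 12 per arm assumes even allocation within Cohort 1. For minimum, maximum and PCS the fault is only that the SAP leaves open whether individual or averaged values are used; the 465 ms example is a consequence of one reading, not of the plan as stated.

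This should be corrected before the ECG tables are programmed. It affects how safety results are read and leaves the efficacy analysis untouched.

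**What to change.** 1. **SAP 6.2.** Exempt scheduled pre- and post-infusion ECG pairs from same-day averaging, state that this exemption takes precedence over the tie rule, and use the pre-dose tracing as the Week 12 value. Cohort 1 then matches Cohort 2, whose Day 85 ECG is pre-dose only.
2. **SAP 11.5.1.** Add Day 1 post-infusion (all subjects, about 100 per arm) and, descriptively, Day 85 post-infusion (Cohort 1, about 12 per arm) as separate time points. Each is change from the pre-first-dose baseline, set against placebo.
3. **SAP 11.5.1 and 11.5.2.** State that minimum, maximum and PCS use every individual post-dose tracing, including Day 1 post-infusion.

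The cost is SAP wording and two extra rows per ECG table; the data are already scheduled for collection. The drawback is low precision on Day 85, which is why that row should be descriptive.

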7.1 Demographic and Baseline Characteristics

The following demographic and baseline characteristics will be summarized for each treatment group, for the combination of all ABBV-8E12 dose groups ("ABBV-8E12 Overall") and for the combination of all treatment groups ("Total Subjects") for the safety dataset.

- Gender (male/female)
- Race (white, black, American Indian/Alaska native, Native Hawaiian or other Pacific Islander, Asian, Other, Multi-Race)
- Education (high school or above, lower than high school)
- Ethnicity (Hispanic or Latino)
- Age (years)
- Age group (< 65, ≥ 65)
- Weight for all subjects (kg)
- Weight for all male subjects (kg)
- Weight for all female subjects (kg)
- Height (cm)
- Body mass index (BMI, kg/m²)
- Body mass index category (BMI, kg/m²) (< 25, ≥ 25)
- APOE allele status (ε2ε2, ε2ε3, ε2ε4, ε3ε3, ε3ε4, ε4ε4)

- Baseline AD medication use: AChEI (donepezil, rivastigmine, galantamine) and memantine

Alcohol and tobacco uses will be summarized for each treatment group, ABBV-8E12 Overall and Total Subjects for the safety dataset. For alcohol use, the number and percentage of subjects who are drinkers, ex-drinkers and non-drinkers (defined as those who have never been a drinker) will be presented. For the tobacco use, the number and percentage of users, ex-users and non-users (defined as those who have never been a user) will be presented. A subject reporting multiple use categories for the different types of tobacco (cigarette, pipe, cigar and chewing tobacco) will be counted in the tobacco user category.

The following baseline efficacy variables will be summarized for each treatment group, ABBV-8E12 Overall and Total Subjects for the ITT dataset.

- CDR-SB score
- ADAS-Cog-14 total score and subscale scores
- FAQ total score
- UPSA-Brief score
- ADCS-MCI-ADL-24 total score
- RBANS total scale score and subtest scores
- MMSE total score
- NPI total score
- ADCOMS score

ADCOMS score is a composite score which is a weighted linear combination of the remaining individual scale items from ADAS-cog, MMSE, and CDR-SB scales. The weights for items are listed below.³

Scale	Item name	Weights
ADAS-cog	Delayed word recall	0.008
	Orientation	0.017
	Word recognition	0.004
	Word finding difficulty	0.016
MMSE	Orientation time	0.042
	Drawing	0.038
CDR-SB	Personal care	0.054
	Community affairs	0.109
	Home and hobbies	0.089
	Judgement and problem solving	0.069
	Memory	0.059
	Orientation	0.078

Categorical variables will be summarized by the number and percentage of subjects in each category and Fisher's exact test will be carried out to assess the comparability between treatment groups. No comparisons of treatment groups will be performed for alcohol and tobacco uses. Continuous variables will be summarized with descriptive statistics (number of non-missing observations, mean, standard deviation, median, minimum and maximum) and no comparisons between treatment groups will be performed.

7.2 Medical History

The conditions/diagnoses recorded in medical/surgery history eCRF will be coded using the most current version of the Medical Dictionary for Regulatory Activities (MedDRA). Data will be summarized and presented using system organ classes (SOCs) and preferred terms (PTs). The SOC will be presented in alphabetical order and the PTs will be presented in alphabetical order within each SOC. The number and percentage of subjects with a particular SOC and PT will be summarized for each treatment group, ABBV-8E12 Overall and Total Subjects for the safety dataset. Subjects reporting more than one PT within a SOC will be counted only once for that SOC. No comparison among treatment groups will be performed.

The following MCI due to AD or AD history variables will be summarized for each treatment group, ABBV-8E12 Overall and Total Subjects for the safety dataset.

- Age at onset of symptoms of cognitive impairment (years)
- Age when first diagnosed as having MCI due to AD or AD (years)
- Years since onset of symptoms of cognitive impairment (Date of Day 1 – Date of onset)
- Years since MCI due to AD or AD diagnosis (Date of Day 1 – Date of diagnosis)
- Family history of AD (None, biological mother, biological father, full sibling, biological child)
- Years of formal education

Categorical variables will be summarized with the number and percentage of subjects in each category. Continuous variables will be summarized with descriptive statistics (number of non-missing observations, mean, standard deviation, median, minimum, and maximum). No comparisons of treatment groups will be performed.

7.3 Previous and Concomitant Medications

Previous medications are defined as all medications with a start date before the first study drug infusion date. Concomitant medications are defined as all medications, other than study drug, taken during the treatment period (i.e., from the first day of study drug administration through 45 days after the last day of study drug administration).

Concomitant medication use for AD or MCI will be summarized into two categories: taken both at baseline and post-baseline, not taken at baseline but taken post-baseline.

Previous and concomitant medications will be coded using the World Health Organization (WHO) dictionary and will be summarized by generic name and Anatomical Therapeutic Chemical (ATC) classification system level 3. The number and percentage of subjects who take at least 1 medication and who take at least 1 dose of each specific medication in the following categories will be summarized for each treatment group, ABBV-8E12 Overall and Total Subjects.

- Previous AD or MCI medication: donepezil, rivastigmine, galantamine, Tacrine, memantine, investigational medicine or other.
- Previous antipsychotic/neuroleptic medications
- Previous anticholinergic medications
- Previous sedatives/benzodiazepines
- Previous Parkinsonian medications
- Concomitant antipsychotic/neuroleptic medications
- Concomitant anticholinergic medications
- Concomitant sedatives/benzodiazepines
- Concomitant Parkinsonian medications
- Concomitant cholinesterase inhibitors (donepezil, rivastigmine, galantamine) or memantine for cognitive impairment.

No comparisons of treatment groups will be performed.

8.0 Subject Disposition

The number of subjects who are screened will be summarized and screen failures will be summarized in Total Subjects and by each reason for screen failures.

For subjects who are randomized in the study, the number and percentage of subjects in each randomization disposition category (randomized but not treated, prematurely discontinued and completed) will be summarized for each treatment group, ABBV-8E12 Overall and Total Subjects.

The number and percentage of subjects who prematurely discontinued study drug or prematurely discontinued from the study will be summarized by reason (primary or any reason) for each treatment group, ABBV-8E12 Overall and Total Subjects.

In addition, the following additional summaries will be presented for all randomized subjects:

- The number and percentage of subjects who are enrolled at each site.

- The number and percentage of subjects who prematurely discontinued at each site.

9.0 Study Drug Exposure and Compliance

Summaries of study drug exposure and compliance will be prepared for the safety dataset.

Study drug exposure will be summarized for each ABBV-8E12 treatment group, ABBV-8E12 Overall. Duration of exposure is calculated as the last study drug administration date minus the first study drug administration date + 30. Total subject years of exposure is calculated by summing the duration of exposure across all subjects and dividing this sum by 365 (1 year will be considered to be 365 days). The number and percentage of subjects who have taken a total of 1, 2, 3, 4 - 6, 7 - 9, 10 - 12, 13 - 15, 16 - 18, 19 - 21, 22 - 24, > 24 infusions of study drug will be summarized. No comparisons of treatment groups will be performed for this summary. In addition, duration of exposure will be summarized with descriptive statistics (number of non-missing observations, mean, standard deviation, median, minimum and maximum duration, and total subject-years).

To evaluate impact of COVID-19 pandemic on study drug compliance, expected infusions (completers are expected to have 24 infusions, prematurely discontinued subjects are expected to have expected number of infusions based on discontinuation visit date) and infusions missed due to COVID-19 pandemic will be summarized for each ABBV-8E12 treatment group and ABBV-8E12 Overall (mean, minimum, maximum of expected infusions; mean, minimum, maximum of missed infusions, mean of the percentage of missed infusions relative to expected number of infusions will be tabulated) across all countries and by country.

At each scheduled dosing visit for ABBV-8E12 groups, the investigator will document whether the subject has received the entire dose infusion or not and the volume administered will be recorded in the eCRF if the entire dose is not administered. The percentage of the assigned dose administered will be calculated at each visit. The mean of

this percentage across infusions for each subject will be obtained. The descriptive statistics (number of non-missing observations, minimum, mean, median, standard deviation, maximum) based on each subject's mean volume percentage of study drug infusion will be summarized for each ABBV-8E12 treatment group and ABBV-8E12 Overall.

